#### 6.4. Visit Windows

Efficacy by-visit summaries will use the analysis visit. Unscheduled and early termination visits will be windowed based on the following analysis visit window which is based on study day. If multiple measurements are taken within the same window, the one taken closest to the target study day will be

used for the analysis. If there are multiple measurements with same difference from target day, the later assessment should be used for the analysis.

Analysis Visit	Target Study Day (relative to first treatment date)	Analysis Visit Window
Baseline	1	<=1
Week 4	29	2 to 42
Week 8	57	43 to 71
Week 12	85	72 to 99
Week 16	113	100 to 141
Week 24 Follow-up	169	> 141

Safety and pharmacokinetics data will not be windowed for by-visit summary. i.e., scheduled visit (including Early Termination visit) data will be used for analysis. For clinical laboratory assessments, if repeated measurements are taken for either time point (scheduled visit), then the last measurement will be used for the value for that time point.

Daily diary efficacy data (CCI ) will be classified into analysis visits as follows. Analysis Visit Target Study Day of Analysis Visit (relative to first treatment date) Baseline 1 Week 1 8 Week 2 15 22 Week 3 Week 4 29 Week 5 36 Week 6 43 Week 7 50 57 Week 8 Week 9 64 Week 10 71 Week 11 78 Week 12 85 92 Week 13 Week 14 99 Week 15 106 Week 16\* 113

These analysis visits will be used in the calculations for all week-based parameters collected on subject's diary data. Other non-diary data, such as, vital signs, body weight, clinical laboratory assessments, respiratory assessment/PEF, will be analyzed according to actual scheduled visits.

Unscheduled labs will be included in listings and considered in the derivation of last, worst post-baseline values, but not summaries of the data by visit.

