9.7.2 Unscheduled Visit

The subject should be reminded to adhere to the study schedule. Unscheduled visits are defined as visits to repeat testing for abnormal laboratory results, for follow-up of AEs, or to conduct efficacy assessments for subjects requiring rescue medication between regularly scheduled study visits. Visits occurring outside of the visit window are not considered unscheduled visits.

Assessments to be conducted at the unscheduled visit will depend on the reason for the visit: Any of the procedures/assessments listed in [Table 4](#) may be conducted, but not all are required. However, blood sample collection for [CCI](#) [REDACTED] are required during unscheduled visits that are conducted for safety reasons.

This document is confidential.

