13.2 Clinical Laboratory Assessments

The hematology laboratory analyses, clinical chemistry laboratory analyses, and urinalyses will be performed at a central laboratory. Reference ranges will be supplied by the central laboratory and used by the investigator to assess the laboratory data for clinical significance and pathological changes.

The investigator or medically qualified sub-investigator must review and evaluate laboratory values for each subject in a timely manner. Study centers should refer to the current version of the laboratory manual for laboratory values outside of normal limits. For each out-of-range laboratory result, the investigator or designee will evaluate whether

This document is confidential.

Page 88 of 133

he/she considers it to be clinically significant, defined as meeting at least 1 of the following conditions:

- The abnormality suggests a disease and/or organ toxicity, or
- The abnormality is of a degree that requires additional active management, eg, discontinuation of the drug, close observation, more frequent follow-up assessments, or further diagnostic investigation.

If the investigator observes a clinically significant laboratory result, the test will be repeated as soon as possible and the subject will be monitored until the value returns to normal and/or an adequate explanation for the abnormality is found.

Investigators will also be allowed to repeat specific laboratory test(s) or procedure(s) where the investigator suspects an inaccuracy or false result and that which may impact the safety of the subject or the interpretation of the trial results; only after discussion with medical monitor.

All clinically significant out-of-range laboratory values at the screening visit will be recorded in the medical history form (report a diagnosis rather than the laboratory value whenever possible). All clinically significant out-of-range laboratory values after the screening visit are to be reported as an AE if this abnormality was not present at the screening visit or is assessed as having worsened since the screening visit (ie, changed significantly from the screening visit). Whenever possible, the investigator should provide a diagnosis of an AE when reporting the abnormal laboratory value.

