### 10.4. Laboratory Evaluations

Clinical laboratory tests are performed at Screening, Baseline, Week 8, Week 16, Follow-up Visit, and Early Termination Visit. All laboratory values will be reported in SI units.

For statistical and graphical summaries of the laboratory tests, values below or above the limit of detection (e.g. '< 3' or '>500') are substituted with the lower limit of detection minus 1% for values below the lower limit and are substituted with the upper limit of detection plus 1% for values above the upper limit (e.g. '< 3' is substituted by '2.97', '> 500' is substituted by '505'). In data listings, the values are shown including the < or > sign.

Results from the central laboratory (hematology, blood chemistry and urinalysis) will be summarized by treatment group and visit using descriptive statistics, including observed values and change from baseline values (for numeric laboratory parameters), distribution of categories (for categorical laboratory parameters). By visit summaries will be performed at all visits (scheduled and ET visits) and for the last post-baseline results during treatment period. Last-post baseline results will include unscheduled visits in the derivation.

In addition, the number and percentage of subjects who met criteria of Potentially Clinically Significant Values (PCSV) will be summarized by treatment group and by visit. Criteria for PCSV are included in Section 20.2.

Shift tables from baseline will be generated by treatment group using the reference ranges at each visit, last post-baseline during treatment period, the worst post-baseline. Hematology, chemistry and applicable urinalysis results will be classified as low (L), normal (N), and high (H) by the laboratory parameter's normal range. Worst post-baseline value is defined the value farthest from the reference range (lower and higher limit). If all post-baseline values are "Normal", the subject is classified as Normal. If any post-baseline value is "Abnormal" ("High" or "Low"), select the farthest one from Lower or Higher limit of reference range.

Distribution of Aspartate Aminotransferase (AST), Alanine Aminotransferase (ALT), Alkaline Phosphatase (ALP), Total bilirubin and Creatinine Phosphokinase (CPK) will be displayed graphically as boxplot by treatment group for each scheduled visit and the maximum post-baseline values.

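### Potentially clinically significant laboratory values are counted by visit only, so those seen only at unscheduled visits or superseded by a same-visit repeat are missing from the counts by arm

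*SAP*

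**What the plan says.** - **Repeats within a visit.** For clinical laboratory tests, SAP 6.4 says that "if repeated measurements are taken for either time point (scheduled visit), then the last measurement will be used" as the value for that visit.
- **Unscheduled results.** The same section says that unscheduled labs are listed and are "considered in the derivation of last, worst post-baseline values, but not summaries of the data by visit".
- **PCSV counts.** SAP 10.4 gives the number and percentage of subjects meeting the criteria: "Potentially Clinically Significant Values (PCSV) will be summarized by treatment group and by visit". The text describes no count over all post-baseline results.
- **Schedule.** SAP 10.4 places laboratory tests at screening, baseline, Week 8, Week 16, follow-up and early termination.
- **Worst value.** SAP 10.4 also plans low/normal/high shift tables with a worst post-baseline category. If any post-baseline value is abnormal, the rule is to "select the farthest one from Lower or Higher limit of reference range".
- **Retesting.** Protocol 13.2 says that after a clinically significant result "the test will be repeated as soon as possible and the subject will be monitored until the value returns to normal". The sentence goes on to allow an adequate explanation as an alternative or additional end point, so it is not a rule to repeat until normal.
- **Where retests are recorded.** Protocol 9.7.2: "Unscheduled visits are defined as visits to repeat testing for abnormal laboratory results", among other reasons.

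**The concern.** The by-visit PCSV table is the only output described that gives PCSV incidence by arm. Two rules restrict what can enter it. Unscheduled results are barred from by-visit summaries, and only the last of several results filed under one scheduled visit is kept. Unscheduled visits are made partly because something looks wrong, and protocol 13.2 calls for a repeat after a clinically significant finding. The results most exposed to the two rules are therefore likely to include abnormal ones.

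Safety is a secondary objective. What is at stake is whether the reported PCSV frequency in each arm covers all laboratory results obtained after baseline or only a subset. The primary vaccine response analysis is not affected.

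**Working it through.** The plan states no figure to reproduce, so the check follows an abnormal post-baseline value through each planned output.

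**Inputs.** The last-value and unscheduled rules come from SAP 6.4. The PCSV, shift, boxplot and listing plans come from SAP 10.4. The retest and adverse event rules come from protocol 13.2, and the definition of an unscheduled visit from protocol 9.7.2.

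| Case | By-visit PCSV count | Worst post-baseline shift | Listings |
|---|---|---|---|
| A. Abnormal value and normal repeat both filed under one scheduled visit | Missed | Unclear | Present |
| B. Abnormal value at a scheduled visit, normal repeat at an unscheduled visit | Counted | Present | Present |
| C. Abnormal value only at an unscheduled visit | Missed | Present | Present |

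**Case A.** The repeat becomes the value for the visit, so the abnormal result leaves the by-visit summary, the by-visit shift and the PCSV count. Whether it still enters worst post-baseline is not settled. SAP 10.4 refers to any post-baseline value, which suggests that it does. SAP 6.4 assigns one value to each time point, which could be programmed so that it does not.

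**Case B.** The unscheduled repeat cannot enter the by-visit tables, so the abnormal scheduled value stays and nothing is lost.

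**Case C.** The value is kept out of the PCSV count but feeds the worst post-baseline shift.

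**Do the other outputs replace the count?**

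- The shift table classifies results as low, normal or high. It does not show whether a PCSV threshold was crossed.
- The maximum post-baseline boxplots cover AST, ALT, ALP, total bilirubin and CPK. They show distributions, not incidence, and include no haematology parameter.
- The PCSV listing gives no rate by arm.
- Adverse event reporting under protocol 13.2 depends on the investigator judging the value clinically significant and new or worsened since screening. PCSV applies fixed criteria.
- The liver event of special interest in protocol 13.1.1 needs ALT or AST above 3 × ULN together with bilirubin above 2 × ULN, so an isolated transaminase rise does not meet it.

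**Size.** Let N be the number of subjects in an arm with any post-baseline PCSV, and U the number whose only PCSV results fall in case A or C. The by-visit table can show at most N − U distinct subjects. The documents give neither N nor U, nor any rate from which to derive them.

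**Direction of the worst value.** The farthest-value rule keeps one direction per subject. With an assumed neutrophil range of 2.0 to 7.5, a value of 0.8 lies 2.0 − 0.8 = 1.2 below and a value of 9.0 lies 9.0 − 7.5 = 1.5 above. That subject is shown as high in the worst-value shift. If the low value was a scheduled result that was not superseded, it still appears in the by-visit shift.

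**The case against.** The strongest reply is that the ordinary retest does no harm. A subject called back for repeat testing attends an unscheduled visit by protocol definition, so the scheduled abnormal value stays in the PCSV count (case B). That stands. It rules out the tempting reading that normal retests routinely overwrite the abnormal results that prompted them. Overwriting needs a repeat filed under the same scheduled visit, and nothing in the documents shows how often that happens.

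A second reply is that abnormalities do not vanish from the safety outputs. This also stands. Unscheduled values expressly feed the last and worst post-baseline results, all laboratory results are listed, and clinically significant values that are new or worsened become adverse events tabulated by arm. A reader might infer that abnormal values drop out of the safety tables altogether. The documents do not support that: the loss is in the by-visit summaries and the PCSV counts, apart from the unclear point in case A.

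Third, a reader might infer that the rules hide a drug–placebo difference. This is not shown. Take assumed counts of 6/123 = 4.9% and 2/123 = 1.6%, and assume half are missed in each arm. The table then shows 3/123 = 2.4% and 1/123 = 0.8%. The difference falls from 3.3 to 1.6 points, but the ratio stays at 3. Every count in this example is invented, including the halving.

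Fourth, taking the last value is a reasonable convention, since protocol 13.2 also allows repeats for a suspected false result. That is accepted, and the by-visit descriptive summaries need no change.

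Finally, the PCSV criteria (SAP 20.2) and the table shells are not in the text available. The PCSV titles in the SAP's index of tables lack the by-visit label that the observed-value and shift tables carry, so a shell might include an overall row. SAP 10.4 does not describe one, and it is the governing text.

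**Conclusion.** The point holds in a limited form. As SAP 10.4 and 6.4 are written, PCSV incidence by arm omits values seen only at unscheduled visits and values superseded by a repeat filed under the same scheduled visit. The gap matters because scheduled post-baseline laboratory tests on treatment are confined to Week 8, Week 16 and early termination, and no other described output gives PCSV incidence by arm. The omission can only lower the counts. By how much, and whether unequally between arms, cannot be determined from the documents.

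The conclusion assumes that the programmed tables follow the SAP text and that no overall PCSV row exists in shells that are not available. It is a worthwhile correction to the safety reporting.

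**What to change.** 1. In SAP 10.4, add an any-time post-baseline PCSV count and percentage by treatment group. Use all results: scheduled, superseded repeats and unscheduled.
2. State in SAP 10.4 that superseded repeats count towards the worst post-baseline value.
3. Optionally, for analytes with both a low and a high limit, show worst-low and worst-high shifts separately.

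Keep the last-value rule in SAP 6.4 for the by-visit descriptive summaries.

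The cost is some SAP wording, slight extra programming and slightly higher reported PCSV rates. The results are already planned for listing, so no new data collection is needed.

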## 6.5. Pooling of Centers

No center pooling is planned.

## 6.6. Subgroups

Subgroup analysis will be performed in an exploratory manner to investigate the treatment effect across various subgroup. The following subgroup analyses will be performed for the primary and secondary vaccine response endpoints:

- By age (<18 years; >=18 years)
- By sex (Male, Female)
- By race (White, Black or African American, Asian, Other)
- CCI
- Baseline Weight (≤Q1, <Q1 median, <median Q3, > Q3)
- Baseline Weight (≤90 kg, > 90 kg)
- Coronavirus disease-19 (COVID-19) Infection (Subjects infected by COVID-19, Subjects not infected)
- Background therapy (subjects with background therapy, subject without background therapy)

In addition, analyses will be performed on the last subgroup (background therapy) for selected secondary efficacy endpoints.

# 7. Demographic, Other Baseline Characteristics and Medication

## 7.1. Subject Disposition and Withdrawals

The screened subjects, screen failures and reasons for screen failures will be summarized in the disposition table.

In addition, the following frequencies (subject number and percent) will be summarized based on ITT Population by treatment group and overall for:

- Randomized subjects
- Subjects treated with at least one dose of study drug
- Subjects who completed treatment (until Week 16)
- Subject who discontinued the treatment and Primary reason for early treatment discontinuation
  - Subject who discontinued from treatment with COVID-19 related reason [This will be identified using Other specify field in CRF]
- Subjects who completed study
- Subject who discontinued the study and Reason for study discontinuation
  - Subject who discontinued from study with COVID-19 related reason [This will be identified using Other specify field in CRF]
- ITT Population (subject number only)
- mITT Population
- SAF Population
- PKAP

The number and frequency will be summarized by site and by treatment group and overall for:

- Subjects screened,
- Screen failure, percentage calculated based on number of screened
- Subjects randomized, percentage calculated based on number of screened
- Subjects treated, percentage calculated based on ITT

Summary of subjects at each visit will be provided by treatment group and overall on ITT population.

The individual time (days) to Permanent Discontinuation of Study Drug by Reason will be presented graphically by treatment group using ITT population. Time to permanent discontinuation is defined as (date of last study drug administration – date of 1st study drug administration + 1).

By-subject listings of eligibility details, randomization details, and withdrawal/study completion details (including reason for discontinuation and duration of treatment prior to discontinuation) will be provided.

A listing of subjects in different analysis population (ITT, mITT, SAF, PKAP) will also be produced.

[figure not shown]
#### 7.2. Protocol Deviations

All protocol deviations will be identified, evaluated, and finalized before the respective database lock (final analysis) and will be discussed in the clinical study report. Protocol deviations will be categorized by type, and whether major or minor based on clinical review and will be determined before database lock. Individual deviations (major and minor) will be presented in a data listing. A summary table for number and percentage of subjects with major protocol deviation and with COVID-19 related deviation will be summarized by type of deviation and treatment group.

# 7.3. Demographic and Other Baseline Characteristics

The following demographic and baseline characteristics will be summarized by treatment group and overall using descriptive statistics for ITT, mITT and safety population:

• Demographics data: Age (years) at screening as continuous and as categorical (12-17 years, >= 18 years), sex, ethnicity, race, height (cm) at screening, body weight (kg) at baseline (overall and by age group), body mass index (overall and by age group).

The stratification factor will also be summarized on ITT and mITT population to show if any discrepancies between what was reported through Interactive Voice Response System (IVRS)/Interactive Web Response System (IWRS) versus baseline value derived using eCRF data.

By-subject listings of demographic data and other baseline characteristics (as summarized above) will be provided.

#### 7.4. Medical History

Medical history will be coded using Medical Dictionary for Regulatory Activities (MedDRA Version 25.0).

Medical history will be summarized by treatment group using the number and percent of subjects reporting each system organ class (SOC) and preferred term (PT) and sorted by descending overall total of SOC and PT. Summary tables will be presented for ITT, mITT, and SAF populations.

Medical history data listings will also be provided.

## 7.5. Medical and Surgical Procedures

Medical and surgical procedures will be coded using MedDRA Version 25.0.

Prior procedures are defined as procedures which stop before 1st injection of study drug. Concomitant procedures are defined as procedures which start or stop on or after the 1st injection of study drug.

Prior and concomitant medical and surgical procedures will be summarized separately by treatment group using the number and percent of subjects reporting each SOC and PT and sorted by descending overall total of SOC and PT. Summary tables will be presented for ITT population.

Medical and surgical procedures will also be listed.

#### 7.6. Medications/Therapies

Prior medications/therapies are defined as medications/therapies which stop before 1st injection of study drug. Concomitant medications/therapies are defined as medications/therapies which start or stop on or after the 1st injection of study drug.

If start and/or stop dates of medications and therapies are missing or partial, the dates will be compared as far as possible with the date of first dose of study drug. Medications and therapies will be assumed to be Concomitant, unless there is clear evidence (through comparison of partial dates) to suggest that they started and stopped prior to the first dose of study treatment. If there is clear evidence to suggest that the medication or medical and surgical procedure started and stopped prior to the first dose of study drug, they will be assumed to be Prior.

For prior and concomitant medications, incomplete (i.e., partial missing) start dates and/or stop dates will be imputed using the algorithm described in Section 6.3.

Medications will be coded using the World Health Organization's Drug Dictionary (WHO DD) Version Global B3 SEP 2019 using the Preferred Anatomical Therapeutic Chemical (ATC) terms. TCI and TCS will be automatically identified using the following rule:

- TCS will be identified by ATC code "D07A".
- TCI will be identified by ATC code "D11AH" and with standardized medication name "TACROLIMUS" and "PIMECROLIMUS".

Prior and Concomitant medications will be summarized separately by Anatomical Therapeutic Chemical (ATC) level 2, level 4, and preferred name in frequency tables using ITT, mITT and safety population. Subjects with more than one medication in a given ATC level and preferred name will be counted only once in that category. It will be sorted in descending frequency of ATC level and of PT within ATC level term.

The following summaries will be produced:

- Prior medication
- Concomitant medication
- Rescue medication during treatment period (ITT Population only)
- Rescue medication during follow-up period (ITT Population only)

Sponsor: Galderma S.A./Galderma R&D, LLC; Protocol No.: RD.06.SPR.118380 V4.0, 06Jul2022

 Background therapy (ITT Population only) consisting of TCS and TCI with start date prior to study drug administration and that are not classified as rescue therapy

All medications will be listed. The background TCS dispensation/receipt will also be listed.

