7 INVESTIGATIONAL PLAN

7.1 Description of Overall Study Design and Plan

This is a randomized, double-blind, placebo-controlled, multi-center, parallel-group study in adult and adolescent subjects (≥ 12 to 54 years) with moderate-to-severe AD. Eligible subjects must have a documented history of inadequate response to topical AD medication(s).

Approximately 245 subjects will be randomized 1:1 to receive either 30 mg nemolizumab (with a 60 mg loading dose) or placebo, stratified by baseline disease severity **CCI** **16.9**.

The study consists of 3 periods with up to 28 weeks total study duration: a 2- to 4-week screening period, a 16-week treatment period, and an 8-week follow-up period (12 weeks after the last study drug injection).

Screening Period

The screening period will evaluate subject eligibility. Subjects will apply a moisturizer at least once daily, beginning at screening. Subjects using a stable regimen of low- or medium-potency TCS with or without topical calcineurin inhibitor (TCI) at the screening visit (ie, ≥ 14 days prior to the baseline visit) should continue their therapy regimen. Subjects not using a stable regimen of TCS with or without TCI at the screening visit should not use these topical therapies during the study unless required as rescue therapy.

Rescue therapies are not permitted during the screening period.

Treatment Period

At the baseline visit, subjects will receive a loading dose of nemolizumab (60 mg) or placebo via 2 subcutaneous injections. Nemolizumab (30 mg) or placebo will then be administered via a single subcutaneous injection Q4W at Week 4, 8, and 12. At the Week 12 visit, subjects will also receive single doses of **PPD** **vaccines**. Clinical assessments will occur according to the schedule of assessments in **Table 4**.

This document is confidential.

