9.6 Prior and Concomitant Therapies

Prior therapies and medications are defined as therapies/medications that have been stopped within the 3 months before the screening visit, unless relevant to the inclusion/exclusion criteria. Whenever possible, all prior therapies/medications for AD and all prior vaccinations should be documented.

Concomitant therapies/medications are defined as follows:

- Any existing therapies ongoing at the time of the screening visit,
- Any changes to existing therapies (such as changes in dose, formulation or application frequency) during the course of the study, or
- Any new therapies received by the subject since the screening visit

The following 2 categories are to be considered for prior and concomitant therapies:

- Drugs/therapies include but are not limited to prescription, over-the-counter, birth control pills/patches/hormonal devices, vitamins, moisturizers, sunscreens, herbal medicines/supplements, homeopathic preparations, and other alternative medications
- Medical and surgical procedures (eg, phototherapy, exodontia). Procedures whose sole purpose is diagnosis (non-therapeutic) are not included

Prior and concomitant therapies or medical/surgical procedures are to be recorded in the appropriate eCRF.

This document is confidential.

Concomitant therapies are to be recorded, reviewed, and updated at each visit.

At each visit, investigators should also confirm concomitant therapies for contraception. Contraceptive counseling should occur at screening or at appropriate visits when pre-pubertal subjects begin menses.

Any new concomitant therapy or modification of an existing therapy may be linked to an AE. In such cases, a corresponding AE form should be completed to account for the new therapy or change in therapy.

Restricted prior therapies are provided in Section [8.2](#).

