9.6.1.1 Topical Background Therapy

At the screening visit (≥ 14 days prior to baseline), subjects who are using a stable regimen of medium- or low-potency TCS therapy, with or without TCI therapy, should continue their therapy regimen.

Background therapy use should be adjusted to the disease activity and tolerability of the subject, including tapering when signs and symptoms improve, discontinuation when lesions clear, and restarting if signs and symptoms recur, at the discretion of the investigator.

Subjects who are not using a stable regimen of topical therapy at the screening visit should not use topical background therapy during the study, unless required as rescue therapy (see Section [9.6.1.3](#)).

Subjects with a history of intolerance to TCS or for whom TCS are not advisable (eg, hypersensitivity, significant skin atrophy) must not use TCS background therapy.

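### SAP 7.6 defines background therapy without requiring that it was still in use, so topicals stopped before Day 1 can count as background therapy

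*SAP*

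**What the plan says.** SAP 7.6 lists a background-therapy summary on the ITT population, "consisting of TCS and TCI with start date prior to study drug administration and that are not classified as rescue therapy". That gives two tests: the start date, and the absence of a rescue classification. There is no condition on stop date, ongoing use, stability of the regimen or potency. The same section does use a stop date elsewhere: "Prior medications/therapies are defined as medications/therapies which stop before 1st injection of study drug". The background rule does not exclude that class.

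SAP 6.6 lists a subgroup, "Background therapy (subjects with background therapy, subject without background therapy"), for the primary and secondary vaccine endpoints, and adds that "analyses will be performed on the last subgroup (background therapy) for selected secondary efficacy endpoints". It gives no definition of its own and does not cite 7.6.

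Protocol 9.6.1.1 ties the term to current use at screening: "subjects who are using a stable regimen of medium- or low-potency TCS therapy, with or without TCI therapy, should continue their therapy regimen". It also says: "Subjects who are not using a stable regimen of topical therapy at the screening visit should not use topical background therapy during the study", rescue excepted. SAP 3.3 carries the same meaning. For subjects not on stable TCS or TCI, Protocol Table 3 sets a two-week period off those products before baseline.

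Two further passages bear on which records will exist. Protocol 7.1 states: "Eligible subjects must have a documented history of inadequate response to topical AD" medication. Protocol 9.6 states: "Whenever possible, all prior therapies/medications for AD and all prior vaccinations should be documented".

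**The concern.** The protocol creates a group of subjects who have used topicals before but are off them at Day 1. They are non-users in the protocol's sense. Under the SAP 7.6 wording, one TCS or TCI record with an early start date is enough to make such a subject a background user, even if the product was stopped well before dosing.

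Two outputs are at stake. Table 14.1.4.3.3 (Summary of Background Therapy) would overstate background use. If the 6.6 subgroup is programmed from the same rule, the with-background group would mix current users with subjects who had stopped, and the without-background group would lose members. Membership would still rest on treatment started before dosing, so the randomised comparison inside each group would survive. What would be lost is the meaning of the labels, and precision in the smaller group. This is the only subgroup in 6.6 that is extended to efficacy endpoints.

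**Working it through.** The documents state no figure on this point, so there is nothing to reproduce. The check is a comparison of definitions, followed by an illustrative count.

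**Definitions side by side**

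| Condition | SAP 7.6 | Protocol 9.6.1.1 / SAP 3.3 |
|---|---|---|
| Started before study drug | yes | implied (in use at screening) |
| In use at screening | not required | required |
| Continued into treatment | not required | required |
| Stable, low or medium potency | not required | required |
| Not rescue | required | background and rescue kept separate |

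Take a subject whose TCS was stopped before screening. The start date precedes study drug and the record is not rescue, so 7.6 counts it as background therapy. Under Protocol 9.6.1.1 the subject is a non-user. The rescue test does not remove the record, because a product stopped before the study is not study rescue. The ATC-code rule in 7.6 does not remove it either, because it identifies the drug class and not whether use is current.

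**Illustrative count**

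Inputs:
- N = 245, planned randomised (SAP 3.5).
- f = true share on background therapy, assumed 0.3 to 0.7.
- q = share of non-users with a stopped TCS or TCI on record, assumed 0.5 to 0.95.

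Neither f nor q is in the documents.

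Formulas:
- misplaced = N(1−f)q
- with-group under 7.6 = Nf + N(1−f)q
- without-group under 7.6 = N(1−f)(1−q)
- without-group under the protocol meaning = N(1−f)

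| f | q | True without | Misplaced | With (7.6) | Misplaced share of with | Without (7.6) |
|---|---|---|---|---|---|---|
| 0.3 | 0.5 | 171.5 | 86 | 159 | 54% | 86 |
| 0.3 | 0.8 | 171.5 | 137 | 211 | 65% | 34 |
| 0.3 | 0.95 | 171.5 | 163 | 236 | 69% | 9 |
| 0.5 | 0.5 | 122.5 | 61 | 184 | 33% | 61 |
| 0.5 | 0.8 | 122.5 | 98 | 220.5 | 44% | 24.5 |
| 0.5 | 0.95 | 122.5 | 116 | 239 | 49% | 6 |
| 0.7 | 0.5 | 73.5 | 37 | 208 | 18% | 37 |
| 0.7 | 0.8 | 73.5 | 59 | 230 | 26% | 15 |
| 0.7 | 0.95 | 73.5 | 70 | 241 | 29% | 4 |

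The extremes in full:
- fewest misplaced: 245 × 0.3 × 0.5 = 36.75, about 37
- most misplaced: 245 × 0.7 × 0.95 = 162.9, about 163
- smallest without-group: 245 × 0.3 × 0.05 = 3.7, about 4
- largest without-group: 245 × 0.7 × 0.5 = 85.75, about 86

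The fewest misplaced and the largest without-group come from different rows. The counts use all randomised subjects. The primary-endpoint subgroup analysis runs on the mITT population, which can be smaller.

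**The case against.** The strongest reply is that the 7.6 wording describes one ITT summary table and not the subgroup. SAP 6.6 does not refer to it, and the primary-endpoint subgroup analysis is on mITT (SAP 8.1.3). SAP Section 9, where the efficacy subgroup may be specified, is not visible. SAP 3.3 also gives a programmer the protocol meaning. Background use may be captured separately: 7.6 mentions a listing of background TCS dispensation or receipt, and Protocol Appendix 4 names background topical therapy as an item apart from concomitant therapies. All of this stands. It makes the effect on the subgroup conditional. It does not rescue the summary table, for which 7.6 is the stated rule, and it leaves 6.6 with no other visible definition.

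A reader might also infer that most entrants must hold a stopped TCS or TCI record and that the without-background group nearly empties. The documents do not support that. The visible entry text says topical AD medication without naming TCS or TCI, recording is only whenever possible, and the usual window for prior therapies is three months before screening unless relevant to eligibility. In the illustration the without-group can still hold up to 86 subjects.

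Nor can the subgroup be called the trial's only view of nemolizumab without topical steroid. Section 9 is not visible, and Protocol 9.6.1.3 allows TCS of any potency as rescue in subjects without TCS background therapy. Even a correctly defined without-group need not be steroid-free.

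**Conclusion.** The point holds in a limited form. Read literally, SAP 7.6 counts topicals stopped before Day 1 as background therapy, which conflicts with Protocol 9.6.1.1 and SAP 3.3. Table 14.1.4.3.3 would overstate background use by an unknown amount. If 6.6 follows the same rule, non-users move into the with-background group. In the illustration 37 to 163 of 245 are misplaced, 18% to 69% of that group, and the without-group falls to between 4 and 86. Those figures rest wholly on the assumed f and q and show sensitivity only.

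A reader might infer that the primary result is in doubt. It is not: the mITT CMH analysis and its sensitivity analyses do not use background status, and SAP 6.6 calls the subgroup analyses exploratory. The wording should still be corrected, because a prespecified subgroup should match its label.

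**What to change.** In SAP 7.6, and by cross-reference in 6.6, define background therapy as a stable low- or medium-potency TCS regimen, with or without TCI, in use at the screening visit and ongoing at first dose (ongoing box ticked, or stop date on or after Day 1), and not flagged as rescue. Assign subjects with only stopped prior TCS or TCI to the without-background group.

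State how stable TCI-only users are classed. Protocol 9.6.1.1 describes TCS with or without TCI, while Table 3 restricts TCI only in subjects not on stable TCI, so the documents leave this open.

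Use status at screening in place of a strict 14-day date test. SAP 6.3 can impute a partial start date to the first-dose date, and a date test would then drop true users.

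The cost is a few sentences of SAP text and an added derivation condition. SAP 6.3 already relies on stop dates and the ongoing box. The potency and stability conditions need product and regimen details. Protocol 9.6 asks for changes in dose, formulation and frequency to be recorded, but the eCRF is not visible, so check that these fields exist before finalising the wording.
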